10.2. Regulatory and Ethical Considerations, Including the Informed Consent Process

Prior to initiation of a site, GSK will obtain favourable opinion/approval from the appropriate regulatory agency to conduct the study in accordance with ICH Good Clinical Practice (GCP) and applicable country-specific regulatory requirements.

The study will be conducted in accordance with all applicable regulatory requirements, and with GSK policy.

The study will also be conducted in accordance with ICH Good Clinical Practice (GCP), all applicable subject privacy requirements, and the guiding principles of the current version of the Declaration of Helsinki. This includes, but is not limited to, the following:

- IRB/IEC review and favorable opinion/approval of the study protocol and amendments as applicable
- Signed informed consent to be obtained for each subject before participation in the study (and for amendments as applicable)

- Investigator reporting requirements (e.g. reporting of AEs/SAEs/protocol deviations to IRB/IEC)
- GSK will provide full details of the above procedures, either verbally, in writing, or both.
- Signed informed consent must be obtained for each subject prior to participation in the study
- The IEC/IRB, and where applicable the regulatory authority, approve the clinical protocol and all optional assessments, including genetic research.
- Optional assessments (including those in a separate protocol and/or under separate informed consent) and the clinical protocol should be concurrently submitted for approval unless regulation requires separate submission.
- Approval of the optional assessments may occur after approval is granted for the clinical protocol where required by regulatory authorities. In this situation, written approval of the clinical protocol should state that approval of optional assessments is being deferred and the study, with the exception of the optional assessments, can be initiated.

10.3. Quality Control (Study Monitoring)

- In accordance with applicable regulations including GCP, and GSK procedures, GSK monitors will contact the site prior to the start of the study to review with the site staff the protocol, study requirements, and their responsibilities to satisfy regulatory, ethical, and GSK requirements.
- When reviewing data collection procedures, the discussion will also include identification, agreement and documentation of data items for which the CRF will serve as the source document.

GSK will monitor the study and site activity to verify that the:

- Data are authentic, accurate, and complete.
- Safety and rights of subjects are being protected.
- Study is conducted in accordance with the currently approved protocol and any other study agreements, GCP, and all applicable regulatory requirements.

The investigator and the head of the medical institution (where applicable) agrees to allow the monitor direct access to all relevant documents

10.4. Quality Assurance

- To ensure compliance with GCP and all applicable regulatory requirements, GSK may conduct a quality assurance assessment and/or audit of the site records, and the regulatory agencies may conduct a regulatory inspection at any time during or after completion of the study.
- In the event of an assessment, audit or inspection, the investigator (and institution) must agree to grant the advisor(s), auditor(s) and inspector(s) direct access to all

relevant documents and to allocate their time and the time of their staff to discuss the conduct of the study, any findings/relevant issues and to implement any corrective and/or preventative actions to address any findings/issues identified.

10.5. Study and Site Closure

- Upon completion or premature discontinuation of the study, the GSK monitor will conduct site closure activities with the investigator or site staff, as appropriate, in accordance with applicable regulations including GCP, and GSK Standard Operating Procedures.
- GSK reserves the right to temporarily suspend or prematurely discontinue this study at any time for reasons including, but not limited to, safety or ethical issues or severe non-compliance. For multicenter studies, this can occur at one or more or at all sites.
- If GSK determines such action is needed, GSK will discuss the reasons for taking such action with the investigator or the head of the medical institution (where applicable). When feasible, GSK will provide advance notification to the investigator or the head of the medical institution, where applicable, of the impending action.
- If the study is suspended or prematurely discontinued for safety reasons, GSK will promptly inform all investigators, heads of the medical institutions (where applicable) and/or institution(s) conducting the study. GSK will also promptly inform the relevant regulatory authorities of the suspension or premature discontinuation of the study and the reason(s) for the action.
- If required by applicable regulations, the investigator or the head of the medical institution (where applicable) must inform the IRB/IEC promptly and provide the reason for the suspension or premature discontinuation.

10.6. Records Retention

- Following closure of the study, the investigator or the head of the medical institution (where applicable) must maintain all site study records (except for those required by local regulations to be maintained elsewhere), in a safe and secure location.
- The records must be maintained to allow easy and timely retrieval, when needed (e.g., for a GSK audit or regulatory inspection) and must be available for review in conjunction with assessment of the facility, supporting systems, and relevant site staff.
- Where permitted by local laws/regulations or institutional policy, some or all of these records can be maintained in a format other than hard copy (e.g., microfiche, scanned, electronic); however, caution needs to be exercised before such action is taken.
- The investigator must ensure that all reproductions are legible and are a true and accurate copy of the original and meet accessibility and retrieval standards, including re-generating a hard copy, if required. Furthermore, the investigator must ensure there is an acceptable back-up of these reproductions and that an acceptable quality control process exists for making these reproductions.

- GSK will inform the investigator of the time period for retaining these records to comply with all applicable regulatory requirements. The minimum retention time will meet the strictest standard applicable to that site for the study, as dictated by any institutional requirements or local laws or regulations, GSK standards/procedures, and/or institutional requirements.
- The investigator must notify GSK of any changes in the archival arrangements, including, but not limited to, archival at an off-site facility or transfer of ownership of the records in the event the investigator is no longer associated with the site.

10.7. Provision of Study Results to Investigators, Posting of Information on Publicly Available Clinical Trials Registers and Publication

Where required by applicable regulatory requirements, an investigator signatory will be identified for the approval of the clinical study report. The investigator will be provided reasonable access to statistical tables, figures, and relevant reports and will have the opportunity to review the complete study results at a GSK site or other mutually-agreeable location.

GSK will also provide the investigator with the full summary of the study results. The investigator is encouraged to share the summary results with the study subjects, as appropriate.

GSK will provide the investigator with the randomization codes for their site only after completion of the full statistical analysis.

The procedures and timing for public disclosure of the results summary and for development of a manuscript for publication will be in accordance with GSK Policy.

A manuscript will be progressed for publication in the scientific literature if the results provide important scientific or medical knowledge.

12. APPENDICES

12.1. Appendix 1 – Abbreviations and Trademarks

Abbreviations

µg.h/mL	Microgram Hours per milliliter
µL	Microliters
AE	Adverse Event
ALP	Alkaline Phosphatase
ALT	Alanine Aminotransferase
AST	Aspartate Aminotransferase
AUC	Area Under the Curve
BUN	Blood Urea Nitrogen
CL	Clearance
CPK	Creatine Phosphokinase
CQ	Chloroquine
CRF	Case Report Form
CV	Cardiovascular
DDI	Drug-drug Interaction
DRE	Disease-Related Event
ECG	Electrocardiogram
eCRF	Electronic Case Report Form
FDA	Food and Drug Administration
g	Grams
g/dL	Grams per Deciliter
G6PD	Glucose-6-phosphate Dehydrogenase
GCP	Good Clinical Practice
GSK	GlaxoSmithKline
Hb	Hemoglobin
hCG	Human Chorionic Gonadotropin
Hct	Hematocrit
HIV	Human Immunodeficiency Virus
ICH	International Conference on Harmonization
IEC	Independent Ethics Committee
INR	International Normalized Ratio
IRB	Institutional Review Board
kg	Kilograms
LDH	Lactate Dehydrogenase
MCV	Mean Cell Volume
MetHb	Methemoglobin
mg	Milligrams
mL	Milliliters
MMV	Medicines for Malaria Venture
MSDS	Material Safety Data Sheet
PK	Pharmacokinetics

PQ	Primaquine
RBC	Red Blood Count
SAE	Serious Adverse Event
SRM	Study Reference Manual
TQ	Tafenoquine
ULN	Upper Limit of Normal
WBC	White Blood Count
WHO	World Health Organization

Trademark Information

Trademarks of the GlaxoSmithKline group of companies
NONE

Trademarks not owned by the GlaxoSmithKline group of companies
None

12.2. Appendix 2: Liver Safety Required Actions and Follow up Assessments

Phase II liver chemistry stopping criteria and required follow up assessments

Liver Chemistry Stopping Criteria – Liver Stopping Event	
ALT-absolute	ALT \geq 5xULN
ALT Increase	ALT \geq 3xULN persists for \geq 4 weeks
Bilirubin^{1, 2}	ALT \geq 3xULN and bilirubin \geq 2xULN (>35% direct bilirubin)
INR²	ALT \geq 3xULN and INR>1.5, if INR measured
Cannot Monitor	ALT \geq 3xULN and cannot be monitored weekly for 4 weeks
Symptomatic³	ALT \geq 3xULN associated with symptoms (new or worsening) believed to be related to liver injury or hypersensitivity
Required Actions and Follow up Assessments following ANY Liver Stopping Event	
Actions	Follow Up Assessments

 • Immediately discontinue study treatment • Report the event to GSK within 24 hours • Complete the liver event CRF and complete an SAE data collection tool if the event also meets the criteria for an SAE² • Perform liver event follow up assessments • Monitor the subject until liver chemistries resolve, stabilize, or return to within baseline (i.e., screening) (see MONITORING below) • Do not restart/rechallenge subject with study treatment unless allowed per protocol and GSK Medical Governance approval is granted • If restart/rechallenge not allowed per protocol or not granted, permanently discontinue study treatment and may continue subject in the study for any protocol specified follow up assessments 	
 • Viral hepatitis serology⁴ • Blood sample for pharmacokinetic (PK) analysis, obtained as soon as possible and within 24 hours after last dose⁵ • Serum creatine phosphokinase (CPK) and lactate dehydrogenase (LDH). • Fractionate bilirubin, if total bilirubin\geq2xULN • Obtain complete blood count with differential to assess eosinophilia • Record the appearance or worsening of clinical symptoms of liver injury, or hypersensitivity, on the AE report form • Record use of concomitant medications on the concomitant medications report form including acetaminophen, herbal remedies, other over the counter medications. • Record alcohol use on the liver event alcohol intake case report form


MONITORING:
 
For bilirubin or INR criteria:
 
 Repeat liver chemistries (include ALT, AST, alkaline phosphatase, bilirubin) and perform liver event follow up assessments within 24 hrs Monitor subjects twice weekly until liver chemistries resolve, stabilize or return to within baseline A specialist or hepatology consultation is recommended 
For All other criteria:
 
 Repeat liver chemistries (include ALT, AST, alkaline phosphatase, bilirubin) and perform liver event follow up assessments within 24-72 hrs Monitor subjects weekly until liver chemistries resolve, stabilize or return to within baseline 	
For bilirubin or INR criteria:
 
 Anti-nuclear antibody, anti-smooth muscle antibody, Type 1 anti-liver kidney microsomal antibodies, and quantitative total immunoglobulin G (IgG or gamma globulins). Serum acetaminophen adduct HPLC assay (quantifies potential acetaminophen contribution to liver injury in subjects with definite or likely acetaminophen use in the preceding week [James, 2009]). NOTE: not required in China Liver imaging (ultrasound, magnetic resonance, or computerised tomography) and /or liver biopsy to evaluate liver disease: complete Liver Imaging and/or Liver Biopsy CRF forms.
---	--

- Serum bilirubin fractionation should be performed if testing is available. If serum bilirubin fractionation is not immediately available, discontinue study treatment for that subject if ALT \geq 3xULN **and** bilirubin \geq 2xULN.. Additionally, if serum bilirubin fractionation testing is unavailable, **record presence of detectable urinary bilirubin on dipstick**, indicating direct bilirubin elevations and suggesting liver injury.
- All events of ALT \geq 3xULN **and** bilirubin \geq 2xULN (>35% direct bilirubin) or ALT \geq 3xULN **and** INR>1.5, if INR measured which may indicate severe liver injury (possible 'Hy's Law'), **must be reported as an SAE (excluding studies of hepatic impairment or cirrhosis)**; INR measurement is not required and the threshold value stated will not apply to subjects receiving anticoagulants
- New or worsening symptoms believed to be related to liver injury (such as fatigue, nausea, vomiting, right upper quadrant pain or tenderness, or jaundice) or believed to be related to hypersensitivity (such as fever, rash or eosinophilia)
- Includes: Hepatitis A IgM antibody; Hepatitis B surface antigen and Hepatitis B Core Antibody (IgM); Hepatitis C RNA; Cytomegalovirus IgM antibody; Epstein-Barr viral capsid antigen IgM antibody (or if unavailable, obtain heterophile antibody or monospot testing); Hepatitis E IgM antibody
- PK sample may not be required for subjects known to be receiving placebo or non-GSK comparator treatments.) Record the date/time of the PK blood sample draw and the date/time of the last dose of study treatment prior to blood sample draw on the CRF. If the date or time of the last dose is unclear, provide the subject's best approximation. If the date/time of the last dose cannot be approximated OR a PK sample cannot be collected in the time period indicated above, do not obtain a PK sample. Instructions for sample handling and shipping are in the SRM.

Phase II liver chemistry increased monitoring criteria with continued therapy

Liver Chemistry Increased Monitoring Criteria – Liver Monitoring Event	
Criteria	Actions
ALT \geq 3xULN and <5xULN and bilirubin <2xULN, without symptoms believed to be related to liver injury or hypersensitivity, and who can be monitored weekly for 4 weeks	
 • Notify the GSK medical monitor within 24 hours of learning of the abnormality to discuss subject safety. • Subject can continue study treatment • Subject must return weekly for repeat liver chemistries (ALT, AST, alkaline phosphatase, bilirubin) until they resolve, stabilise or return to within baseline (i.e., screening) • If at any time subject meets the liver chemistry stopping criteria, proceed as described above • If, after 4 weeks of monitoring, ALT <3xULN and bilirubin <2xULN, monitor subjects twice monthly until liver chemistries normalize or return to within baseline.

References

12.3. Appendix 3: Definition of and Procedures for Recording, Evaluating, Follow-Up and Reporting of Adverse Events

12.3.1. Definition of Adverse Events

Adverse Event Definition:

- An AE is any untoward medical occurrence in a patient or clinical investigation subject, temporally associated with the use of a medicinal product, whether or not considered related to the medicinal product.
- NOTE: An AE can therefore be any unfavorable and unintended sign (including an abnormal laboratory finding), symptom, or disease (new or exacerbated) temporally associated with the use of a medicinal product.

Events meeting AE definition include:

- Any abnormal laboratory test results (hematology, clinical chemistry, or urinalysis) or other safety assessments (e.g., ECGs, radiological scans, vital signs measurements), including those that worsen from baseline, and felt to be clinically significant in the medical and scientific judgement of the investigator.
- Exacerbation of a chronic or intermittent pre-existing condition including either an increase in frequency and/or intensity of the condition.
- New conditions detected or diagnosed after study treatment administration even though it may have been present prior to the start of the study.
- Signs, symptoms, or the clinical sequelae of a suspected interaction.
- Signs, symptoms, or the clinical sequelae of a suspected overdose of either study treatment or a concomitant medication (overdose per se will not be reported as an AE/SAE unless this is an intentional overdose taken with possible suicidal/self-harming intent. This should be reported regardless of sequelae).
- "Lack of efficacy" or "failure of expected pharmacological action" per se will not be reported as an AE or SAE. However, the signs and symptoms and/or clinical sequelae resulting from lack of efficacy will be reported if they fulfil the definition of an AE or SAE.
- The signs and symptoms and/or clinical sequelae resulting from lack of efficacy will be reported if they fulfil the definition of an AE or SAE. Also, "lack of efficacy" or "failure of expected pharmacological action" also constitutes an AE or SAE.

Events NOT meeting definition of an AE include:

- Any clinically significant abnormal laboratory findings or other abnormal safety assessments which are associated with the underlying disease, unless judged by the investigator to be more severe than expected for the subject's condition.
- The disease/disorder being studied or expected progression, signs, or symptoms of the disease/disorder being studied, unless more severe than expected for the subject's condition.
- Medical or surgical procedure (e.g., endoscopy, appendectomy): the condition that leads to the procedure is an AE.
- Situations where an untoward medical occurrence did not occur (social and/or convenience admission to a hospital).
- Anticipated day-to-day fluctuations of pre-existing disease(s) or condition(s) present or detected at the start of the study that do not worsen.

12.3.2. Definition of Serious Adverse Events

If an event is not an AE per definition above, then it cannot be an SAE even if serious conditions are met (e.g., hospitalization for signs/symptoms of the disease under study, death due to progression of disease, etc).

Serious Adverse Event (SAE) is defined as any untoward medical occurrence that, at any dose:**a. Results in death****b. Is life-threatening**

NOTE:

The term 'life-threatening' in the definition of 'serious' refers to an event in which the subject was at risk of death at the time of the event. It does not refer to an event, which hypothetically might have caused death, if it were more severe.

c. Requires hospitalization or prolongation of existing hospitalization

NOTE:

- In general, hospitalization signifies that the subject has been detained (usually involving at least an overnight stay) at the hospital or emergency ward for observation and/or treatment that would not have been appropriate in the physician's office or out-patient setting. Complications that occur during hospitalization are AEs. If a complication prolongs hospitalization or fulfills any other serious criteria, the event is serious. When in doubt as to whether "hospitalization" occurred or was necessary, the AE should be considered serious.
- Hospitalization for elective treatment of a pre-existing condition that did not worsen from baseline is not considered an AE.

d. Results in disability/incapacity

NOTE:

- The term disability means a substantial disruption of a person's ability to conduct normal life functions.
- This definition is not intended to include experiences of relatively minor medical significance such as uncomplicated headache, nausea, vomiting, diarrhea, influenza, and accidental trauma (e.g. sprained ankle) which may interfere or prevent everyday life functions but do not constitute a substantial disruption

e. Is a congenital anomaly/birth defect**f. Other situations:**

- Medical or scientific judgment should be exercised in deciding whether reporting is appropriate in other situations, such as important medical events that may not be immediately life-threatening or result in death or hospitalization but may jeopardize the subject or may require medical or surgical intervention to prevent one of the other outcomes listed in the above definition. These should also be considered serious.
- Examples of such events are invasive or malignant cancers, intensive treatment in an emergency room or at home for allergic bronchospasm, blood dyscrasias or convulsions that do not result in hospitalization, or development of drug dependency or drug abuse

g. Is associated with liver injury and impaired liver function defined as:

- $ALT \geq 3xULN$ and total bilirubin* $\geq 2xULN$ (>35% direct), **or**
- $ALT \geq 3xULN$ and $INR^{**} > 1.5$.

* Serum bilirubin fractionation should be performed if testing is available; if unavailable, measure urinary bilirubin via dipstick. If fractionation is unavailable and $ALT \geq 3xULN$ and total bilirubin $\geq 2xULN$, then the event is still to be reported as an SAE.

** INR testing not required per protocol and the threshold value does not apply to subjects receiving anticoagulants. If INR measurement is obtained, the value is to be recorded on the SAE form.

- Refer to [Appendix 2](#) for the required liver chemistry follow-up instructions

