4.4.1. Dose Justification in Cohort Aged <2 years

There is no lower age limit below which infants and children are not susceptible to vivax malaria. There is, however, a balance to be struck in terms of collecting data sufficient to define an appropriate dose for infants, versus limiting the number of study related assessments to which this highly vulnerable group are subjected. Where possible, PK data from an additional cohort of six infants aged ≥ 6 months to <2 years (weighing ≥ 5 kg) will be obtained to define dosing in infants down to 6 months. Available data from this cohort will be combined with data obtained from the main cohort as part of the final population PK analysis. The lower age of 6 months is based on the age at which G6PD enzyme activity reaches maturity. The pediatric population PK model used for dose prediction has been developed based on adult patient data and includes an allometric function for weight-based dosing. Allometric scaling accounts for size differences only and not age-related changes in metabolizing enzymes or renal function. However, the generalized functional immaturity in metabolizing enzyme activity and renal function approach adult levels about 6 months after birth [Kearns, 2003]. Thus, the model is appropriate for dose prediction in this cohort.

The decision to enrol subjects aged ≥ 6 months - <2 years will be based on a review of exposure data as well as of safety results from the first interim analysis. Particular attention will be paid to the reporting of adverse events related to decreases in hemoglobin (Hb), methemoglobin (metHb) levels, increases in creatinine, and any reports of phototoxicity.

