4.6.1. Risk Assessment

Potential Risk of Clinical Significance	Summary of Data/Rationale for Risk	Mitigation Strategy
Investigational Product (IP) – SB-252263		
Hemolysis in G6PD-deficient subjects (PRIMARY RISK)	Tafenoquine is an 8-aminoquinoline, a class of drug known to exert oxidative effects on Hb. In patients with G6PD deficiency (or other disorders of erythrocytic pentose phosphate pathway of glucose metabolism) hemolysis is expected due to RBCs lack of capacity to protect itself against oxidative effects of such drugs. Hemolysis has been reported in G6PD deficient patients inadvertently recruited into previous TQ studies.	
 All subjects with <70% G6PD activity will be excluded. Subjects with Hb levels <8 g/dL will also be excluded. Protocol-defined SAE criteria will be adopted; defined as, ≥ 3.0 g/dL or 30% decline in Hb from the baseline value, or a Hb value <6 g/dL, to aid in safety monitoring. Recommendations for clinical management of hemolysis will be provided as part of investigator training.
Methemoglobinemia (metHb)	Methemoglobinemia has been observed in previous studies associated with larger total doses of TQ than are being considered for clinical investigation. Risk factors have been assessed and include a strong relationship between MetHb development, TQ dose, and body surface area. The doses recommended for this study, designed to achieve similar levels of exposure observed in adults treated with 300mg TQ, should pose minimal risk of causing elevations of metHb of clinical concern.	
 Methemoglobin percentage will be monitored non-invasively at selected times throughout the study.
High Systemic Exposure to TQ	In a cohort of patients taking 600 mg TQ (first part of Study TAF112582) the highest AUC(0- ∞) observed was 275 $\mu\text{g}\cdot\text{h}/\text{mL}$.	
 The presence of an observed AUC(0-∞) in any subject of >275 $\mu\text{g}\cdot\text{h}/\text{mL}$ will trigger a review of dosing in the study.
Liver Transaminase Elevations	Preclinical repeat dose toxicology studies observed liver changes that were fully or partially reversible. During the TQ thorough QT study (TAF114582)	
 Conduct liver function tests – baseline and Day 8. TQ dose limited to 300mg total dose equivalent in pediatric subjects.

Potential Risk of Clinical Significance	Summary of Data/Rationale for Risk	Mitigation Strategy

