7.5.1.1. Protocol-Defined SAE

Hemoglobin decreases of $\geq 30\%$ of >3 g/dL from baseline; or, an overall drop in Hb below 6.0 g/dL in the first 15 days of the study should be reported as an SAE.

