7.5.6. Clinical Safety Laboratory Assessments

Clinical chemistry and hematology samples will be analyzed by local laboratories. All protocol required laboratory assessments must be conducted in accordance with the Laboratory Manual, and Protocol Time and Events Schedule (Section 7.1).

Hematology tests will be conducted on the Day 1, 3 and 8 visits. Clinical chemistry tests will be conducted on the Day 1 and Day 8 visits. In addition, laboratory tests may be conducted at any time during the study, as warranted by the condition of the subject and at the investigator's discretion. All laboratory results that are considered clinically significant should be recorded as AEs. The panel of tests to be analyzed are detailed below in Table 3 and Table 4. All laboratory data will be used for the purpose of safety analysis and reporting for this study.

Table 3 Hematology Tests

Hemoglobin	Hematocrit	Platelets	MCV
WBC	RBC	Reticulocyte	WBC Differential

Table 4 Clinical Chemistry Tests

Creatinine	BUN	Total bilirubin	Indirect bilirubin
AST	ALT	ALP	CPK

Hemoglobin and/or Hct measurements that deviate substantially from previous readings should be immediately repeated via venous sampling. If a significant drop in Hb or Hct is observed, all additional hematology and clinical chemistry labs should be obtained immediately. In addition, a blood sample should be drawn for G6PD genotyping (see Section 7.7).

Methemoglobin status will be assessed at Day 1 and Day 8. Subjects with anemia may have symptomatic methemoglobinemia (e.g., blue discoloration of skin and lips, shortness of breath) at levels lower than subjects with normal hemoglobin levels

(symptoms typically do NOT occur with MetHb values <20% in subjects with normal hemoglobin levels).

All laboratory tests with values that are considered clinically significantly abnormal during participation in the study should be repeated until the values return to normal or baseline. If such values do not return to normal within a period judged reasonable by the investigator, the etiology should be identified and the sponsor notified.

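### Appendix 3 (12.3.1–12.3.2) conflicts with the protocol-defined hemoglobin SAE in Section 7.5.1.1, so a site could withhold that SAE for a fall it attributes to malaria and judges no worse than expected

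*Protocol*

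**What the plan says.** **The study-specific rule.** Protocol Section 7.5.1.1 sets numeric hemoglobin triggers: a relative or absolute fall from baseline, and a floor. On the floor it says "an overall drop in Hb below 6.0 g/dL in the first 15 days of the study should be reported as an SAE". Nothing there depends on what caused the fall. The risk table in Section 4.6.1 gives the same device as mitigation for hemolysis ("Protocol-defined SAE criteria will be adopted; defined as", followed by thresholds). Section 7.5.6 adds, for laboratory results generally, "All laboratory results that are considered clinically significant should be recorded as AEs".

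**The general definitions.** Section 7.5.1 points investigators to Appendix 3 for what counts as an AE or SAE. Section 12.3.1 lists among events that are not AEs "Any clinically significant abnormal laboratory findings or other abnormal safety assessments which are associated with the underlying disease", with the exception "unless judged by the investigator to be more severe than expected" for the subject's condition. Section 12.3.2 opens with "If an event is not an AE per definition above, then it cannot be an SAE even if serious conditions are met". Its criteria (a) to (g) include a numeric liver criterion at (g) but no hemoglobin criterion.

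**Use of the reports.** Section 7.5.1.2 requires SAEs to reach the sponsor within 24 hours. For the decision to open the infant cohort, Section 4.4.1 says "Particular attention will be paid to the reporting of adverse events related to decreases in hemoglobin".

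**The concern.** Two parts of the protocol give different answers for the same child. Under 7.5.1.1 a fall past the threshold is reported and its cause is considered afterwards. Under Appendix 3 the investigator's view of cause and expectedness can decide whether there is an event to report at all.

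Attribution to malaria is readily available here. Every subject has vivax malaria. Section 4.6.2 says the parasite itself produces hemolysis, and Section 2.1.1 describes severe anemia as fairly common in younger children with the infection. The trial has a single arm, so no control group helps separate disease from drug. At stake are the prompt notice that the protocol-defined SAE provides, the AE and SAE counts that reach the interim and final tables, and whether sites report the same fall in the same way.

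**Working it through.** No figure in the plan needs reproducing. The check is a comparison of texts, plus one small calculation on the SAP displays.

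**1. Follow one fall through the protocol.** Take a fall that meets 7.5.1.1, which the investigator attributes to malaria and judges no more severe than expected.

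| Text | Result |
|---|---|
| 7.5.1.1 | SAE; cause not asked |
| 7.5.6 | AE if clinically significant; no exclusion for disease |
| 12.3.1, exclusion list | Not an AE |
| 12.3.2, first sentence | Not an AE, so cannot be an SAE |
| 12.3.2, criteria (a)–(g) | Hemoglobin criterion not listed |

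If the investigator instead judges the fall more severe than expected, 12.3.1 no longer excludes it. The conflict therefore needs both judgements: attribution to malaria, and no more severe than expected.

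**2. Look for text that settles it.**
- No sentence says whether 7.5.1.1 or Appendix 3 prevails.
- The inclusion list in 12.3.1 covers clinically significant laboratory results that worsen from baseline. The exclusion list also starts from clinically significant results and takes out the disease-associated ones, so the inclusion list does not resolve the conflict.
- The disease-related event terms in 7.5.1.6 are pyrexia, chills, rigor and headache, with a positive slide. A hemoglobin fall is not among them, so a fall excluded under 12.3.1 has no obvious event page.

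**3. Check what survives without an SAE report.** The SAP takes hemoglobin from laboratory values whether or not an event was filed:
- a listing of clinically relevant drops (8.4.1);
- change categories (Tables 3.28–3.29) and declines over the first 10 days (Tables 3.30–3.31);
- boxplots that include every subject's nadir up to the Day 8 visit (Figure 3.2);
- profile plots for all subjects at each interim (8.4.2).

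**4. Check the floor criterion in those displays.** The F2 flag (SAP 10.8.1), the plot of enzyme activity against maximum fall, and the final-analysis profile plots (8.4.2) select on a drop above 30 g/L or of at least 30%. The profile plots also take G6PD-deficient subjects. None of them uses a value below 6 g/dL.

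- Lowest eligible hemoglobin (5.1): 8.0 g/dL. Example nadir: 5.9 g/dL.
- Absolute drop: 8.0 − 5.9 = 2.1 g/dL = 21 g/L, which is not above 30.
- Relative drop: 2.1 / 8.0 = 26%, which is below 30.

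This child meets the floor in 7.5.1.1 but neither SAP drop criterion. The child still appears in the general hematology tables, in Figure 3.2 and in the category above 20 and up to 30 g/L, but is not marked as past a threshold.

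The gap is narrow. A value below 6.0 g/dL can escape the 30% rule only if baseline is below 6.0 / 0.70 = 8.57 g/dL, so it concerns baselines from 8.0 to about 8.57 g/dL. At a baseline of 8.0 the 30% limit is 0.70 × 8.0 = 5.6 g/dL, so the nadirs missed lie between 5.6 and 6.0 g/dL.

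**The case against.** The strongest reply is that a specific rule governs a general one. Section 7.5.1.1 is headed as protocol-defined, follows directly on the pointer to Appendix 3, and adds a numeric trigger with no attribution test. Section 4.6.1 repeats that it will be used. Section 12.3.5 already treats the natural history of the disease as an alternative cause to weigh once an AE exists, which implies that such falls are expected to be recorded. Many sites would read it this way. That stands as the natural reading, but it is not written down, and the opening of 12.3.2 makes no exception.

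Three stronger readings are tempting, and the documents do not support them.

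- **That Appendix 3 cancels the hemoglobin SAE whenever malaria is blamed.** It does not: the exception for findings more severe than expected remains, and 7.5.1.1 remains in force as text. This is an unresolved conflict.
- **That the main hemolysis signal is lost.** Section 3 of the protocol names clinically relevant hemoglobin drops as a key safety endpoint, listed separately from AE incidence, and the SAP analyses them from laboratory data. The first interim includes change categories and every subject's hematology profile, so the infant-cohort decision does not rest on AE reports alone. Section 7.5 also provides for monthly safety review, although it does not say which laboratory data are seen.
- **That an unreported fall leaves no G6PD genotype.** Only footnote j of the Time and Events table ties the sample to an SAE. Sections 7.5.6 and 7.7 call for it after a hemoglobin decline without that condition.

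**Conclusion.** The point holds as a conflict of wording with a limited consequence. A site applying Appendix 3 literally could decline to file a protocol-defined hemoglobin SAE when the investigator attributes the fall to malaria and finds it no more severe than expected. A site applying 7.5.1.1 would file it.

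The consequence is confined to AE and SAE counts (for example final Tables 3.1, 3.15 and 3.20, of which the first two are also interim displays), the 24-hour report, and comparability between sites. The laboratory-based hemoglobin analyses are intact, apart from the narrow floor gap shown above, where the SAE report is the route that marks the child as past a threshold.

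The documents give no expected rate of threshold falls or of attribution to malaria, so no number of affected reports can be stated. The conclusion assumes that a site could reasonably treat Appendix 3 as the governing definition, which Section 7.5.1 invites. It does not depend on the exact thresholds, which Sections 4.6.1 and 7.5.1.1 word differently. It is worth correcting because the rule is listed mitigation for the stated primary risk in children, and correcting it is cheap.

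**What to change.** Reconcile the passages:

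1. In the 12.3.1 exclusion for disease-associated laboratory findings, and in the first sentence of 12.3.2, state that a hemoglobin fall meeting 7.5.1.1 is recorded as an AE and reported as an SAE whatever cause the investigator assigns. Causality is already assessed separately under 12.3.5, so no new step is needed.
2. List the criterion in 12.3.2 beside liver criterion (g), by reference to 7.5.1.1.
3. Make 7.5.6 and 12.3.1 agree on whether other clinically significant laboratory results associated with malaria are AEs.

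The cost is a protocol wording change, a memo to sites, and a few additional SAE reports for falls that turn out to be due to malaria. No dose, threshold, eligibility rule or analysis changes.
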